#### 5. INTRODUCTION

## 5.1 Background and Rationale

Several candidate genes related to dopamine and noradrenergic neurotransmitter systems are associated with attention deficit hyperactivity disorder (ADHD) severity and subtypes (persistence, comorbidity, functional impairment, and treatment effects), such as *DAT1*, *DRD4*, *MAO-A*, *ADRA2A*, *ADRA2C*, *NET*, and *COMT*. Recently, a large-scale, genome-wide study comparing copy number variations (CNVs) in 3,500 ADHD cases versus approximately 13,000 controls revealed that rare, recurring CNVs impacting specific glutamate receptor metabotropic (GRM) genes (ie, *GRM1*, *GRM5*, *GRM7*, and GRM8) were found in patients with ADHD at significantly higher frequencies compared to healthy controls.

Originally developed by Nippon Shinyaku Co., fasoracetam monohydrate (NFC-1, previously referred to as NS-105) is an important candidate to explore for use in restoring metabotropic glutamate receptors (mGluRs) activity in patients with ADHD exhibiting mGluR hypofunction. It has been shown to improve symptoms of depression and memory/learning in animal models. The drug activity is based on regulating the intracellular adenylyl cyclase-activity stimulated by mGluRs and works by inhibiting the brain gamma-aminobutyric acid B (GABA) receptor stimulus response and enhancing the beta-adrenergic receptor response and the acetylcholine-mediated neurologic system response (1).

Data from animal models, pharmacotherapeutic interventions, and brain and genetic studies in humans implicate glutamatergic system involvement in ADHD pathophysiology. Interventions specifically targeting this system remain to be developed even though a recent, large-scale, genome-wide study revealed that rare, recurring CNVs impacting genes in the glutamatergic network (ie, *GRM1*, *GRM5*, *GRM7*, and *GRM8*) were detected in approximately 10% of the total ADHD cases (2).

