## 8.2 Study Entry Criteria

#### 8.2.1 Inclusion Criteria

A subject will be eligible for study participation if the subject meets all of the following criteria:

- 1. Subject is male or female,  $\geq 12$  to  $\leq 17$  years of age.
- 2. Subject has a body mass index in the range of  $\geq 15$  to  $\leq 35$  kg/m^2.
- 3. Subject has ADHD as defined by DSM-5 and ADHD-RS- $5 \ge 28$  at Baseline with or without conventional ADHD therapy.
- 4. Subject has an intelligence quotient (IQ) > 79, based on the Wechsler Abbreviated Scale of Intelligence, second edition (WASI-II).
- 5. Subject has been genotyped previously and determined to have disruptive mutations in genes within the GRM-network as determined by the presence of CNVs (GRM biomarker-positive subjects). The confirmation of a subject's positive status will be provided by the sponsor.
- 6. Subject is a non-smoker and/or has not used nicotine or nicotine-containing products on a weekly or more frequent basis for at least approximately 6 months.
- 7. Subject is judged to be in general good health, other than having ADHD, based on medical history, physical examination, vital signs measurements, laboratory safety tests, and the C-SSRS performed at the Screening Visit and/or prior to administration of IP.
- 8. Female subjects of reproductive potential will have a negative pregnancy test at Screening (serum) and prior to drug administration (urine). If sexually active, female subjects agree to use (and/or have her partner use) 2 acceptable methods of birth control beginning at least 2 weeks prior to administration of IP and throughout the study. Acceptable methods of

- birth control are abstinence or 2 of the following: intrauterine device, diaphragm, spermicides, cervical cap, contraceptive sponge, and condoms.
- 9. Subject has no clinically significant abnormality on ECG performed at the Screening Visit and/or prior to administration of IP such as serious arrhythmia, bradycardia, tachycardia, cardiac conduction problems, or other abnormalities deemed to be a potential safety issue.
- 10. Parent/legal guardian and subject understand the study procedures and agree to the subject's participation in the study as indicated by parental/legal guardian signature on the subject informed consent form and subject signature on the assent form.

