# 13.1.3 Safety Endpoints

Adverse events will be coded using the most recent version of the Medical Dictionary for Regulatory Affairs (MedDRA) and tabulated by system organ class and preferred term. Adverse events will be analyzed by frequency, severity, relationship to IP, and their effect on participation in the study.

Clinical laboratory values will be compared to normal ranges and flagged for levels of clinical concern. The analysis will focus on the frequencies of abnormal values as well as within-subject changes observed during the course of the study.

Vital signs and ECG recordings will also be examined for changes during the study that may be attributed to exposure to IP.

The C-SSRS will also be examined for changes that may be attributed to exposure to IP.

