9.3 Vital Signs

Descriptive summaries of actual (absolute) values and changes from baseline will be presented for systolic and diastolic blood pressure, pulse, respiratory rate, and BMI. These tables will be grouped by treatment group, and by visit.

Additionally, the frequency and percentage of subjects with values of Potential Clinical Importance (PCI) will be summarized in shift tables, by treatment group and overall for each study visit. Criteria for assigning PCI to vital signs are as follows:

SAP FINAL Version 2.0

Criteria for PCI Vital Signs and Change in Body Weight						
Measurement	Lower Criterion	Upper Criterion				
Systolic BP	< 90 mmHg	>120 mmHg				
Diastolic BP	< 50 mmHg	>80 mmHg				
Pulse Rate	≤ 50 bpm	≥ 130 bpm				
Respiration Rate	< 10 breaths/minute	>20 breaths/minute				
Body Weight Change	≥ 7% decrease	≥ 7% increase				

Vital signs and weight/height measurements will also be presented in a subject listing.

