9.4 Electrocardiograms

ECG results will be summarized in three ways, as follows:

- 1. A summary of Central ECG results that presents the number and percent of results that are deemed normal, abnormal, and missing.
- 2. A summary providing N and % of evaluations that are interpreted by each investigative site as Normal, Abnormal NCS, Abnormal CS, and missing.
- 3. Tabulation of ECG results that are of potential clinical importance. Criteria for assigning PCI to ECG results are as follows:

Criteria for PCI categories to ECG Results							
ECG Parameter	Lower Criterion	Upper Criterion					
Heart Rate	≤ 50 bpm	≥ 130 bpm					
PR Interval	None	≥ 180 msec					
QRS Interval	None	≥ 100 msec					
QT Interval	None	≥ 450 msec					
QTcB	None	≥ 450 msec					
QTcF	None	≥ 450 msec					
Change in Heart Rate	≤ 50 bpm	None					
	with decrease > 5 bpm						
Change in QTcB	None	≥ 30 msec					
Change in QTcF	None	≥ 30 msec					

Depending on the incidence of abnormal ECG results, some of these displays might not be needed.

ECG results will also be displayed in a separate subject listing.

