Missing	xx(xx.x%)	xx (xx x%)	xx (xx.x%)	xx (xx x%)	xx (xx x%)	xx (xx x%)	xx (xx.x%)	xx (xx x%)
Low	xx (xx.x%)	xx (xx x%)	xx (xx.x%)	xx (xx x%)	xx (xx x%)	xx (xx x%)	xx (xx.x%)	xx (xx x%)
Normal	xx (xx.x%)	xx (xx x%)	xx (xx.x%)	xx (xx x%)	xx (xx x%)	xx (xx x%)	xx (xx.x%)	xx (xx x%)
High	xx(xx.x%)	xx (xx x%)	xx (xx.x%)	xx (xx x%)	xx (xx x%)	xx (xx x%)	xx (xx.x%)	xx (xx x%)

{Continue for all scheduled postbaseline visits and all analytes. Start a new page for every additional analyte}

Note: Percentages are 100*n/N. A low value is a result less than the lower normal reference range; A high value is a result greater than the normal reference range; A normal value is a result which falls between the low and high normal reference ranges.

Source: Listing 16.2.7.1

^[1] Baseline value is on the column, post-baseline value is on the row.

T:\Medgenics\NFC-1\ADHD-201\...\xxx.sas run on DDMMMYYYY at HH:MM on data extracted on DDMMMYYYY

Table 14.3.3.5

Shifts from Baseline of Clinical Laboratory Data: Hematology by Randomized Treatment Safety Population

{Similar shell as Table 14.3.3.4; Source: Listing 16.2.7.2}

Table 14.3.3.6

Shifts from Baseline of Clinical Laboratory Data: Urinalysis by Randomized Treatment Safety Population

{Similar shell as Table 14.3.3.4; Source: Listing 16.2.7.3}

Table 14.3.4.1
Summary of Vital Signs by Randomized Treatment by Study Visit
Safety Population

{Similar shell as Table 14.3.3.1; Source: Listing 16.2.8}

Protocol: MDGN-NFC1-ADHD-201

Page 1 of x Final

Table 14.3.4.2 Potentially Clinically Important Vital Signs by Randomized Treatment Safety Population

Parameter		
Visit	NFC-1	Placebo
Category	(N=xx)	(N=xx)
Temperature (°F)		
Baseline		
n	XX	XX
< 96 °F	xx (xx x%)	xx (xx x%)
\geq 96 °F and \leq 102°F	xx (xx x%)	xx (xx x%)
> 102°F	xx(xxx%)	xx (xx x%)
Missing	xx (xx x%)	xx (xx x%)
Visit 3		
n	XX	XX
< 96 °F	xx (xx x%)	xx (xx x%)
\geq 96 °F and \leq 102°F	xx (xx x%)	xx (xx x%)
> 102°F	xx (xx x%)	xx (xx x%)
Missing	xx (xx x%)	xx (xx x%)

{Continue for all scheduled post-baseline visits and all parameters. Start a new page for every additional parameter, individual parameter ranges are given within the SAP text Section 9.3}

Source: Listing 16.2.8

Page 1 of x Final

Table 14.3.5.1
Incidence of Abnormal ECG Findings: based on Site Interpretations by Randomized Treatment by Study Visit
Safety Population

Visit	NFC-1	Placebo
Category	(N=xx)	(N=xx)
Baseline		
n	XX	XX
Normal	xx (xx x%)	xx (xx.x%)

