Abnormal – Not Clinically Significant	xx (xx x%)	xx (xx.x%)
Abnormal – Clinically Significant	xx (xx x%)	xx (xx.x%)
Unable To Be Evaluated	xx(xxx%)	xx (xx.x%)
Visit 3		
n	XX	XX
Normal	xx (xx x%)	xx (xx.x%)
Abnormal – Not Clinically Significant	xx (xx x%)	xx (xx.x%)
Abnormal – Clinically Significant	xx (xx x%)	xx (xx.x%)
Unable To Be Evaluated	xx(xxx%)	xx (xx.x%)
Visit 4		
n	XX	XX
Normal	xx (xx x%)	xx (xx.x%)
Abnormal – Not Clinically Significant	xx (xx x%)	xx (xx.x%)
Abnormal – Clinically Significant	xx (xx x%)	xx (xx.x%)
Unable To Be Evaluated	xx (xx x%)	xx (xx.x%)

Note: Percentages are 100*n/N. ECG = Electrocardiogram.

Source: Listing 16.2.9

Page 1 of x

Final

Medgenics, Inc.

Protocol: MDGN-NFC1-ADHD-201

Table 14.3.5.2
Incidence of Abnormal ECG Findings: based on Central Reading by Randomized Treatment by Study Visit
Safety Population

Visit	NFC-1	Placebo
Category	(N=xx)	(N=xx)
Baseline		
n	XX	XX
Normal	xx(xxx%)	xx (xx.x%)
Abnormal	xx(xxx%)	xx (xx.x%)
Unable To Be Evaluated	xx (xx x%)	xx (xx.x%)
Visit 3		
n	XX	XX
Normal	xx (xx x%)	xx (xx.x%)
Abnormal	xx (xx x%)	xx (xx.x%)
Unable To Be Evaluated	xx (xx x%)	xx (xx.x%)
Visit 4		
n	XX	XX
Normal	xx (xx x%)	xx (xx.x%)
Abnormal	xx (xx x%)	xx (xx.x%)
Unable To Be Evaluated	xx (xx x%)	xx (xx.x%)

Note: Percentages are 100*n/N. ECG = Electrocardiogram.

Source: Listing 16.2.10

T:\Medgenics\NFC-1\ADHD-201\...\xxx.sas run on DDMMMYYYY at HH:MM on data extracted on DDMMMYYYY

CONFIDENTIAL AD-ST-33.03 16 Mar 2012

Protocol: MDGN-NFC1-ADHD-201

Page 1 of x Final

Table 14.3.5.3
Potentially Clinically Important ECG Results by Randomized Treatment
Safety Population

Parameter		
Visit	NFC-1	Placebo
Category	(N=xx)	(N=xx)
Heart Rate		
Baseline		
n	XX	XX
≤ 50 bpm	xx (xx x%)	xx (xx x%)
> 50 bpm and < 130 bpm	xx (xx x%)	xx (xx x%)
≥ 130 bpm	xx (xx x%)	xx (xx x%)
Unable To Be Evaluated	xx (xx x%)	xx (xx x%)
Visit 3		
n	XX	XX
≤ 50 bpm	xx (xx x%)	xx (xx x%)
> 50 bpm and < 130 bpm	xx (xx x%)	xx (xx x%)
≥ 130 bpm	xx (xx x%)	xx (xx x%)
Unable To Be Evaluated	xx (xx x%)	xx (xx x%)

{Continue for all scheduled post-baseline visits and all parameters. Start a new page for every additional parameter, individual parameter ranges are given within the SAP text Section 9.4}

Source: Listing 16.2.9

Protocol: MDGN-NFC1-ADHD-201

Page 1 of x Final

Table 14.3.6 Summary of C-SSRS Assessments by Randomized Treatment Safety Population

	NFC-1	Placebo	Overall
Category [1]	(N=xx)	(N=xx)	(N=xx)

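### The heart-rate change criterion in SAP 9.4 has no upward entry and pulse has no change criterion, so the only upward flag is 130 bpm or more and no table counts subjects with a large increase by arm (minor)

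*SAP*

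**What the plan says.** SAP 9.4 lists the PCI criteria for ECG results. Heart rate has absolute limits on both sides, 50 bpm or less and 130 bpm or more. The row labelled "Change in Heart Rate" has a lower criterion of 50 bpm or less "with decrease > 5 bpm" and the entry None on the upper side. In the same table, change in QTcB and change in QTcF each have an upper criterion of 30 msec or more.

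SAP 9.3 gives pulse the same two absolute limits and no change criterion. Body weight in that table has a change criterion in both directions (7%).

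The shell for Table 14.3.5.3 in SAP Appendix A places all values "> 50 bpm and < 130 bpm" in a single category. The heart-rate block it shows has no change row.

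Outside the PCI tables, SAP 9.3 says: "Descriptive summaries of actual (absolute) values and changes from baseline will be presented for systolic and diastolic blood pressure, pulse, respiratory rate, and BMI". The shell for that table, 14.3.4.1, is given only as "Similar shell as Table 14.3.3.1; Source: Listing 16.2.8", and the model table has no change-from-baseline column. Protocol 13.1.3 states the aim without a direction: "Vital signs and ECG recordings will also be examined for changes during the study that may be attributed to exposure to IP".

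**The concern.** A PCI table is there to count individual outliers that a group mean can hide. For heart rate it can count falls to 50 bpm or less, but on the upward side it counts only readings of 130 bpm or more. A subject who goes from 65 to 125 bpm at rest appears in neither Table 14.3.4.2 nor Table 14.3.5.3 as a PCI value.

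This departs from the pattern elsewhere in the two criteria tables, where QTc and body weight have upward change criteria. It also fits poorly with a protocol that looks for changes in general and names "serious arrhythmia, bradycardia, tachycardia, cardiac conduction problems" among the ECG abnormalities that bar entry.

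At stake is how a nearly empty row would be read. If few or no subjects reach 130 bpm in either arm, the table may be taken as evidence of no heart-rate increase when it had little chance of showing one. SAP 9.4 adds that some ECG displays might be dropped depending on how many abnormal results there are.

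**Working it through.** The documents give no expected flag rate and no heart-rate data, so there is no figure of the plan's own to reproduce.

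**Step 1: what the change row adds.** Its lower entry requires a value of 50 bpm or less and a fall of more than 5 bpm. Any such value already meets the absolute limit of 50 bpm or less. A subject going from 56 to 50 bpm is flagged by the absolute limit with or without the change row. The upper side has no entry. The row therefore adds no newly flagged subject in either direction.

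**Step 2: the rise needed for a flag.** The required rise is 130 minus baseline: 60 bpm from 70, 50 bpm from 80, 40 bpm from 90.

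**Step 3: share flagged at one reading.**
- From the documents: limit 130 bpm (SAP 9.3, 9.4); about 45 subjects per arm (Protocol 7.1); six post-baseline visits with ECG and vital signs, Visits 3 to 8 (Protocol 17.1).
- Assumed: normally distributed resting heart rate, mean 75 and SD 12 bpm (central); mean 85 and SD 14 (upper case); a mean rise of 20 bpm.
- Formula: P = 1 − Φ((130 − mean − rise)/SD).
- Central: (130 − 75 − 20)/12 = 2.917, P = 0.18%; 45 × 0.00177 = 0.08 subjects per visit.
- Upper case: (130 − 85 − 20)/14 = 1.786, P = 3.7%; 45 × 0.0371 = 1.7 subjects per visit.

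With the central mean and SD, other rises give 0.009% at +10 bpm, 0.04% at +15 and 1.9% at +30.

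**Step 4: share flagged at any of six visits.** Simulation with a within-subject correlation of 0.6 between visits (assumed) and a mean rise of 20 bpm:

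| Resting mean / SD | Any visit ≥ 130, rise of 20 | Any visit ≥ 130, no rise |
|---|---|---|
| 70 / 10 | 0.02% | 0.00% |
| 75 / 12 | about 0.8% | 0.00% |
| 85 / 14 | about 13% (0.13 × 45, about 6 subjects) | 0.3% |

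**Step 5: what an upward change entry would do.** These cut-offs only show sensitivity; no document supports a particular value. In the central case, 100 bpm or more with a rise of 20 bpm or more at any visit would flag about 59% of subjects under a mean rise of 20 bpm and 1.9% with no drug effect. Relaxing the rise to 15 bpm flags about 3.4% of subjects with no drug effect in the central case and about 17% (0.17 × 45, about 8 subjects) in the upper case.

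**Step 6: whether other displays fill the gap.** A comparison of mean pulse change would be sensitive to a shift. At 45 per arm and a true difference of 10 bpm, power is Φ(10/(SD × √(2/45)) − 1.96). With an assumed SD of change of 15 this is Φ(3.16 − 1.96) = 89%; with SD 10 it is Φ(4.74 − 1.96) = 99.7%. But a mean does not count subjects, the shell for Table 14.3.4.1 copies a layout without change columns, and SAP 9.4 plans no continuous summary of ECG heart rate.

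**The case against.** The case for leaving the plan alone has several good parts.

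- **Limits on both sides.** A reader might infer from the empty cell that the heart-rate limits as a whole are one-sided. They are not: ECG heart rate and pulse both have an upper absolute limit. Only the change row lacks an upward entry. This stands.
- **Pharmacology.** Protocol 5.1 describes the drug as "enhancing the beta-adrenergic receptor response", and a reader might infer an expected rise in heart rate. The sentence concerns brain receptor systems, also names GABA-B and acetylcholine, and states no cardiac effect or direction. Inclusion criterion 9 names bradycardia beside tachycardia, and exclusion criterion 6 names bradycardia but not tachycardia. The documents support looking in both directions; they do not show that a rise is likely.
- **Counts are not always near zero.** A reader might infer that the PCI tables would be empty whatever the drug does. The upper case in the working contradicts that.
- **Other displays.** The site reading (Table 14.3.5.1) and central reading (Table 14.3.5.2) can count an ECG at 125 bpm as abnormal. Protocol 10.3.3.2.2 requires clinically relevant ECG changes to be reported as adverse events. Pulse summaries include the maximum, and Listing 16.2.8 shows individual values. A large rise would not be invisible. What remains is that none of these gives a count by arm of subjects with a large increase.
- **Weight.** Safety is descriptive (Protocol 13.4.4), the PCI analyses were added in the SAP (section 10), and no decision rule uses them. This limits the severity.

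**Conclusion.** The gap is real but minor. The change row for heart rate flags nobody beyond the absolute limits, pulse has no change row, and an increase is counted only at 130 bpm or more. With a mean rise of 20 bpm, that limit would catch about 0.8% of subjects at any visit in the central case and about 13% in the upper case. These figures rest on an assumed normal distribution, an assumed rise and an assumed visit correlation of 0.6, none of which comes from the documents. The textual point does not depend on them.

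The documents do not support saying that a heart-rate increase would go unnoticed or that the drug is expected to cause one. They support the narrower conclusion that the planned tables contain no count, by arm, of subjects with a large increase.

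**What to change.** Before unblinding:

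1. In SAP 9.4, replace None in the upper cell of the heart-rate change row with an increase-from-baseline criterion.
2. In SAP 9.3, add a change row for pulse with a criterion in each direction.
3. Keep 130 bpm or more as a separate category.
4. Show the new rows in the shells for Tables 14.3.4.2 and 14.3.5.3.

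The sponsor's safety physician should set the cut-offs without knowledge of treatment. They are reporting flags and change no treatment rule.

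The cost is one filled cell, one added row and two edited shells, using measurements already scheduled at baseline and every treatment visit. The downside is chance flags in both arms, of the size shown in step 5 of the working. Reporting both arms side by side lets the reader judge them.

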9.5 Columbia Suicide Severity Rating Scale (C-SSRS)

The C-SSRS score will be summarized by treatment group and overall for each study visit it is measured. These C-SSRS evaluations will be presented in a subject listing.

9.6 Physical Examination Findings

Abnormal physical examination findings at screening and indications of clinically significant abnormal findings that were newly diagnosed or worsened since the screening visit will be provided in a subject listing.

SAP FINAL Version 2.0

9.7 Concomitant Medication

Concomitant medications will be analyzed the same way as prior medications as noted in Section 7.3. The frequency and percentage of all concomitant medications will be summarized by ATC classification level 3 and preferred term for all patients in the Safety population by treatment group and overall. Similarly to previous, post-treatment medications will be analyzed the same way as prior medications as noted in Section 7.3.

Page 20 of 88

A subject listing of all medications will be provided.

9.8 Exposure and Compliance

For each subject, treatment compliance will be calculated at each visit and summarized for the entire study. Overall compliance will be summarized by treatment group. Compliance is defined in Section 6.3. Drug Accountability/Exposure and Treatment compliance will also be provided in a subject listing.

10 CHANGES FROM PLANNED ANALYSIS

Below are the major changes and/or updates from the protocol planned analysis:

- The SAP has ANCOVA with LOCF as the primary endpoint but this was noted as ANOVA in the protocol
- CGI-I and CGI-S were originally going to be analyzed by ANOVA, but will be analyzed by a Chi-Square test
- PCI analyses has been added for ECG, Vitals
- Post-treatment AEs and Post-treatment medications have been added
- Several tables now include dose group summaries instead of NFC-1 vs. Placebo

SAP FINAL Version 2.0

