## 9.5 Method of Assigning Subjects to Treatment Groups

In this parallel-group randomized study, subjects who meet study entry criteria will be randomly assigned in a 1:1 ratio to NFC-1 or placebo. The randomization schedule will be computergenerated using a permuted block algorithm and will randomly allocate IP to randomization numbers. The randomization numbers will be assigned sequentially through the central IWRS as subjects are entered into the study.

The randomization schedule will be prepared by in advance of study initiation. All efforts will be made to ensure the integrity of the study blind up until the final database has been locked. No one involved in study conduct will have access to the randomization schedule prior to that event. No subject will be randomized into this study more than once.

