# 13.2 Sample Size Determination

Enrollment of 90 subjects is expected to yield 80 subjects who complete the study as planned. Assuming an effect size of 0.7, this number will provide approximately 90% power to detect a significant difference between the treatments based on a 2-tailed  $\alpha = 0.05$  comparison of mean change from Baseline.

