## 13.4.3.2 Secondary Analyses

Secondary efficacy analyses will examine the effects of the treatment on changes observed in other efficacy measures (ie, CGI-S, ASHS, and SCARED). These analyses will model the overall or total scale scores and will employ the same general approach as for the primary analysis. All secondary efficacy measures will be treated as continuous measurement scales and analyzed by the ANOVA methods described above.

Results of the CGI-I assessment will also be dichotomized and presented for each week of treatment. CGI-I scores of 1 or 2 will be combined into a single group labelled "Improved" and scores of 3 to 7 will be combined and labelled "No Improvement." The observed proportions of "Improved" subjects will be compared between treatment groups at each week of the study.

In addition, analysis of the weekly results from ADHD-RS-5 and CGI-I will be evaluated for evidence of trend over time. This analysis will employ a linear mixed-effects model with repeated measures on each subject. Terms for the model will be selected as described for the primary analysis.

Secondary analyses will focus on the ITT Population. However, analyses of the PP Population may be performed if warranted by the data.

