6 GENERAL ISSUES FOR STATISTICAL ANALYSIS

6.1 General Statistical Methodology

Data processing, tabulation of descriptive statistics, calculation of inferential statistics, and graphical representations will be performed using SAS® Software (release 9.3 or higher) for Windows, unless otherwise specified.

Continuous (quantitative) variables will be summarized using descriptive statistics including number of non-missing values, mean, standard deviation (SD), median, minimum, and maximum. Where appropriate, estimates will be presented with 95% confidence intervals (CIs).

Categorical (qualitative) variables will be summarized using the number and proportion of each possible value. In general, the denominator for the percentage calculation will be based upon the total number of subjects in the study population for the treatment group. 95% CIs of proportions may also be presented for selected endpoints where applicable. Zero-count levels of variables will not display a percentage.

The minimum and maximum will be reported with the same degree of precision (i.e., the same number of decimal places) as the raw data. Measures of location (mean and median) will be

SAP FINAL Version 2.0

reported to 1 degree of precision more than the raw data and measures of spread (standard deviation) will be reported to 2 degrees of precision more than the raw data.

All statistical tests will be conducted at the 0.05 significance level using 2-tailed tests, and P-values will be reported. Assessments done on unscheduled visits will not be summarized but will be listed.

Page 12 of 88

In general, baseline and safety tables will be completed for the Safety Population unless otherwise specified. Efficacy tables for primary and secondary endpoints will be presented for the ITT Population. However, analyses of the PP Population may be performed if warranted by the data. These potential PP tables are not present in the table index.

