8.2 Secondary Analysis

Secondary analysis endpoints will include the following measurements (ASHS and SCARED treated as continuous measures):

- Improvement in CGI-I/CGI-S
- Change from baseline in ASHS total score
- Change from baseline in SCARED total score

When appropriate, the analysis for these endpoints will employ the same model and approach as in the primary analysis using an ANCOVA as specified above. Additionally, any subscales for the above primary/secondary endpoints will be included on their corresponding table for the total score (i.e. ADHD-RS-5 Inattention subscale, SCARED Generalized Anxiety, etc.). Please see Section 6.3 for a complete list of derived subscales and composite scores.

Results of the CGI-I assessment will be dichotomized and presented by count and frequency for each week of treatment. CGI-I scores of 1 (very much improved) or 2 (much improved)will be combined into a single category labeled 'Improved', and all other scores (3 [minimally improved] to 7 [very much worse]) will be combined into a single category labeled 'Not Improved'. The

SAP FINAL Version 2.0

observed frequencies of 'Improved' subjects will be compared using a chi-square analysis to test the hypothesis of no association between Improvement and Treatment at type I error rate of 5%.

Page 17 of 88

The CGI-S assessment will be presented similarly. CGI-S scores of 1 (Normal, not at all ill) or 2 (Borderline mentally ill) will be combined into a single category labeled 'Normal or Borderline mentally ill', and all other scores (3 [Mildly Ill] to 7 [Among the most extremely ill patients]) will be combined into a single category labeled 'Mentally ill'.

As to measure treatment response and remission of subjects, three criteria will be defined for each [4]. For response, the criteria are (A) a change in ADHD-RS-5 total score from baseline of 30% or more, (B) a CGI-I score of 1 (very much improved) or 2 (much improved) relative to baseline, and (C) a composite requiring both (A) and (B) to be met. For remission, the criteria are (A) ADHD-RS-5 total score of 18 or less at post-baseline visits, (B) a CGI-I score of 1, and (C) a composite of (A) and (B) to be met. The observed frequency and percentage of subjects in each category will be presented and will be compared using a chi-square analysis to test the hypothesis of no association between response/remission and treatment for each category.

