11.2 Planned Table Shells

Table	Table Title	Topline
14.1.1	Disposition of Study Population by Optimized Dose and Randomized Treatment (ITT Population)	х
14.1.2	Major Protocol Deviations (ITT Population)	
14.1.3	Demographics and Baseline Characteristics by Optimized Dose and Randomized Treatment (Safety Population)	х
14.1.4	Disease Characteristics at Baseline by Optimized Dose and Randomized Treatment (Safety Population)	х
14.1.5	Summary of Prior Medications by Randomized Treatment (Safety Population)	
14.2.1.1	Analysis of Change from Baseline in ADHD-RS-5: Total Score and Subscales, by Study Visit (ITT Population)	х
14.2.1.2	Summary of Change from Baseline in ADHD-RS-5 Score and Subscales by Actual Dose and Randomized Treatment, by Study Visit (ITT Population)	
14.2.2.1	Chi-Square Analysis of CGI-I Improvement, by Study Visit (ITT Population)	х
14.2.2.2	Summary of Categorical and Continuous CGI-I Scores by Randomized Treatment Group and Study Visit (ITT Population)	х
14.2.2.3	Summary of CGI-I Improvement by Optimized Dose and Randomized Treatment, by Study Visit (ITT Population)	
14.2.3.1	Chi-Square Analysis of CGI-S Improvement, by Study Visit (ITT Population)	
14.2.3.2	Summary of Categorical and Continuous CGI-S Scores by Randomized Treatment Group and Study Visit (ITT Population)	
14.2.3.3	Summary of CGI-S Improvement by Optimized Dose and Randomized Treatment, by Study Visit (ITT Population)	
14.2.4.1	Analysis of Change from Baseline in ASHS Total Score and Factors, by Study Visit (ITT Population)	
14.2.4.2	Summary of Change from Baseline in ASHS Total Score and Factors by Randomized Treatment, by Study Visit (ITT Population)	
14.2.5.1	Analysis of Change from Baseline in SCARED Score and Factors, by Study Visit (ITT Population)	
14.2.5.2	Summary of Change from Baseline in SCARED Score and Factors by Randomized Treatment, by Study Visit (ITT Population)	
14.2.6.1	Chi-Square Analysis of Response and Remission Criteria, at End of Study (ITT Population)	х
14.3.1.1	Summary of TEAEs by Dose at Onset (Safety Population)	
14.3.1.2	Incidence of TEAEs by Dose at Onset and Randomized Treatment (Safety Population)	х
14.3.1.3	Incidence of TEAEs occurring in more than 5% of subjects by Randomized Treatment (Safety Population)	

SAP FINAL Version 2.0

14.3.1.4	Incidence of Post-Treatment AE's by Randomized Treatment (Safety Population)	
14.3.1.5	Incidence of SAE's by Randomized Treatment (Safety Population)	

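### The SAP drops the protocol's full-scale analyses of CGI-I and keeps only chi-square tests on cut scores; one prespecified full-scale test should stand beside them.

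*SAP*

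**What the plan says.** Protocol 13.4.3.2 sets a general rule: "All secondary efficacy measures will be treated as continuous measurement scales and analyzed by the ANOVA methods described above". It then says that CGI-I will additionally be split into Improved (1-2) and No Improvement (3-7), with the proportions compared between arms each week. It also plans a linear mixed-effects model with repeated measures for the weekly ADHD-RS-5 and CGI-I results.

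SAP 8.2 keeps the split. The Improved frequencies "will be compared using a chi-square analysis to test the hypothesis of no association between Improvement and Treatment". The same cut returns as Response criterion B and within composite C, and a score of 1 serves as Remission criterion B; these too are tested by chi-square. SAP 10 records the change: "CGI-I and CGI-S were originally going to be analyzed by ANOVA, but will be analyzed by a Chi-Square test".

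Table 14.2.2.2 shows the seven CGI-I levels with mean and SD but no test. MMRM is in the SAP abbreviation list, but no such model is specified in the text, and SAP 10 does not list its removal. Tables 14.2.2.1 and 14.2.2.2 are both flagged topline in SAP 11.2.

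**The concern.** CGI-I is the trial's only global rating of change. A split at 2|3 cannot register movement from no change to minimally improved, or from much to very much improved. If treatment moves patients along the whole scale, a test on the split discards information that a small phase 2 trial has already collected and that its protocol meant to use. One of the two lost analyses also went unreported, so a reader of SAP 10 would not know that the protocol had planned a longitudinal CGI-I model.

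**Working it through.** **Does the SAP leave any full-scale CGI-I test?** SAP 8.2 offers the primary ANCOVA to secondary endpoints when appropriate, but labels only ASHS and SCARED as continuous. That ANCOVA adjusts for the baseline value of the outcome, and CGI-I has none: it is first rated at Visit 3. Every specified CGI-I test is therefore a chi-square on a cut score.

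**Inputs from the documents**
- "All statistical tests will be conducted at the 0.05 significance level using 2-tailed tests" (SAP 6.1).
- "Enrollment of 90 subjects is expected to yield 80 subjects who complete the study as planned" (Protocol 13.2), with subjects "randomly assigned in a 1:1 ratio to NFC-1 or placebo" (Protocol 9.5): 45 randomized or 40 completers per arm.
- "Assuming an effect size of 0.7, this number will provide approximately 90% power to detect a significant difference between the treatments" (Protocol 13.2). This concerns mean change from baseline, so it fits ADHD-RS-5 and cannot describe CGI-I.

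**The plan's own figure.** Normal approximation: power = Φ(0.7·√(n/2) − 1.96).
- n = 45: Φ(3.320 − 1.960) = 91.3% (t test 90.7%).
- n = 40: Φ(3.130 − 1.960) = 87.9% (t test 87.1%).

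The stated 90% reproduces with all 90 randomized and falls 2 to 3 points short with 80 completers.

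**CGI-I under a uniform shift.** The documents give no CGI-I effect, SD or response rate. Assumptions: a normal latent scale cut into seven categories, a shift of 0.7 borrowed from the figure above, and a placebo improved rate p0. The active rate is then p1 = Φ(Φ⁻¹(p0) + 0.7).

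Worked case, p0 = 25%, n = 40:
- p1 = Φ(−0.674 + 0.7) = 51%; difference 0.26; pooled rate 0.38.
- z = [0.26·√40 − 1.96·√(2·0.38·0.62)] / √(0.25·0.75 + 0.51·0.49) = (1.644 − 1.345)/0.661 = 0.45.
- Power = Φ(0.45), about 67%. Simulation gives 68%.

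Simulated power at 40 per arm (uncorrected chi-square; Wilcoxon on the seven levels):

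| Placebo improved rate | Chi-square | Wilcoxon | Loss (points) |
|---|---|---|---|
| 15% | 61% | 83% | 22 |
| 25% | 68% | 83% | 15 |
| 35% | 72% | 83% | 11 |
| 45% | 71% | 83% | 12 |

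ANOVA, the method actually dropped, gives 81-85% in the same model over placebo rates of 10-50%.

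**Sensitivity**
- 45 per arm, shift 0.7: ANOVA against chi-square loses about 14 to 20 points for placebo rates of 15-50%.
- Shifts of 0.4 to 0.8 with placebo rates of 10-50%: about 8 to 30 points.
- 40 observed plus 5 missing per arm counted as Not Improved (the Table 14.2.2.1 footnote), shift 0.7: chi-square 60-67%, a loss of 16 to 23 points for placebo rates of 15-45%.

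**CGI-I when the effect sits at the cut.** Assume placebo proportions of 5/20/25/35/10/4/1% over scores 1 to 7, and that treatment moves 40% of those scoring 3 or 4 to a score of 2. The improved rate goes from 25% to 25% + 0.4 × 60% = 49%. At 40 per arm, chi-square power is 61%, Wilcoxon 34% and ANOVA 26%. The improved rates are close to the worked case above (25% and 51%), yet the ranking of the tests reverses.

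**The case against.** The case for leaving the SAP alone has several sound parts.

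- **The split is not the SAP's invention.** A reader might infer that the SAP replaced a continuous analysis with a dichotomy. It did not: the protocol already had the same cut and the same between-arm comparison. The SAP removed the companion analyses and named the test.
- **The protocol is not explicit about an ANOVA for CGI-I.** Its named list is CGI-S, ASHS and SCARED. But its general sentence covers all secondary measures, and SAP 10 itself says that an ANOVA of CGI-I had been planned, which settles the reading.
- **CGI-I has no special rank.** A reader might take it for the main supporting endpoint. Protocol 13.1.2 lists it among unranked secondaries, the synopsis omits it from the secondary list, and SAP 6.4 sets no hierarchy. The topline flag is the most the documents offer, and the response/remission table shares it.
- **The loss is not a document figure.** A reader might infer that the chi-square is simply the weaker test. That holds for a uniform shift and fails for an effect at the cut; the documents do not say which to expect.
- **The dropped ANOVA is disclosed**, and no power is promised for any secondary endpoint.

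All of this limits the point. It argues against demoting the 1-2 versus 3-7 comparison, which the protocol requires and which Response criteria B and C reuse. It does not justify having no full-scale test, and it does not cover the unlisted removal of the mixed model.

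**Conclusion.** The point holds as a cheap improvement. The SAP leaves CGI-I with tests on cut scores only; SAP 10 reports the dropped ANOVA without a reason and omits the dropped mixed model. Under a uniform latent shift of 0.7 and placebo improved rates of 15-45%, relying on the chi-square alone costs about 11 to 22 points of power at 40 per arm. Both inputs are assumptions. Because the ranking of the tests reverses for an effect concentrated at 2|3, the conclusion is that the plan should carry both kinds of test, not that the chi-square is wrong. Nothing here changes the primary ADHD-RS-5 analysis or its power.

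**What to change.** - In SAP 8.2 and Table 14.2.2.2, add one prespecified full-scale CGI-I test at Visit 8: for example a proportional-odds model with treatment and baseline CGI-S (collected at Visit 2), or the protocol's ANOVA or mixed model.
- State how missing Visit 8 scores are handled in that test, including whether an early-termination rating counts. At present the Table 14.2.2.1 footnote counts missing as Not Improved, Table 14.2.6.1 uses non-missing denominators, and SAP 6.2 rules out imputation beyond the items it lists. These should be reconciled.
- Keep the 1-2 versus 3-7 chi-square and the Response criteria as they are.
- Name the main CGI-I test before unblinding, so that the choice cannot follow the results.
- Restore the CGI-I mixed model, or list its removal in SAP 10 with a reason.

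The cost is SAP wording and one result in an existing table, from data already collected. The downsides are one more unadjusted secondary p-value, and an odds ratio or rank test that is harder to read than a responder rate, which is why the rate stays.
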